#### 2.2 Secondary Objectives

- For Cohorts 1-3 (Cohorts 1-2 active IP and Cohort 3 is placebo)
  - Demonstrate target protective concentration (NAC) value  $> 0.02$  U/mL (BoNT/A) or  $> 0.03$  U/mL (BoNT/B) at Day 120
  - To evaluate pharmacodynamic (PD) and anti-drug antibody (ADA) at pre-dose through the end of study
- Cohort 4 (only active IP)
  - Demonstrate target protective concentration (NAC) value of BoNT/A and BoNT/B at 2 hours post-dose
  - To assess pharmacokinetics (PK) at pre-dose through end of study
  - To evaluate pharmacodynamics (PD) and anti-drug antibody (ADA) at pre-dose through the end of study

#### 2.3 Exploratory Objective

- For Cohorts 1-3 (Cohorts 1-2 active product and Cohort 3 is placebo), to evaluate PK parameters to ensure ADA evaluation adequate of the two lots

### 3 Study Design

#### 3.1 General Study Design

This is a Phase 2, randomized, double-blind, placebo-controlled, multicenter trial to evaluate the safety, tolerability, pharmacokinetics (PK), pharmacodynamics (PD), and immunogenicity (ADA) of G03-52-01, administered by a 2-dose-regimen (Days 1 and 45) IM injections for Cohorts 1-3 and a 1-dose regimen (Day 1) for Cohort 4, in adult subjects.

In Cohorts 1-3, approximately 375 subjects between the ages of 18 and 65 years will be randomized in a 1:1:1:1:1 ratio to 5 parallel treatment groups, which constitute 3 cohorts with 150 subjects each for the two dosing cohorts (Cohort 1 50 mg G03-52-01 and Cohort 2 100 mg G03-52-01) and 75 subjects for the Cohort 3 Placebo group. Within each active dosing cohort, subjects will be randomized 1:1 to receive product from active drug Lot 1 or Lot 2. There is no lot within the Placebo cohort.

In Cohort 4, approximately 250 subjects between the ages of 18 and 65 years will be randomized in a 4:1 ratio to 2 treatment groups, which constitutes 1 cohort (Cohort 4) with 200 subjects randomized into the active group (Cohort 4 100 mg G03-52-01) and 50 subjects randomized into the Cohort 4 Placebo group.

Details regarding the planned assessments for each cohort can be found in the Study Treatments and Assessments section.

See Table 1 below for further details.

[figure not shown]

## Statistical Analysis Plan (SAP)

**Table 1: Details of Study Cohorts**

Study Cohort	Expected Number of Subjects	Dosing Day(s)	Drug Product Lot	Group
Cohort 1 50 mg G03-52-01	150	1, 45	Lot 1 (n=75)	Group 1 50 mg Lot 1
			Lot 2 (n=75)	Group 2 50 mg Lot 2
Cohort 2 100 mg G03-52-01	150	1, 45	Lot 1 (n=75)	Group 3 100 mg Lot 1
			Lot 2 (n=75)	Group 4 100 mg Lot 2
Cohort 3 Placebo	75	1, 45	NA	Group 5 Placebo
Cohort 4 100 mg G03-52-01	200	1	NA	Group 6 100 mg
Cohort 4 Placebo	50	1	NA	Group 7 Placebo
Total	625			

**Figure 1: Study Design**

1. Numbers of time points collected are presented in the parentheses.

## 3.2 Key Eligibility Criteria

### 3.2.1 Inclusion Criteria

All must be answered yes for the subject to be eligible for study participation.

1. Informed consent understood and signed prior to screening procedures.
2. Assessed by the Investigator to be a healthy male or healthy, non-pregnant, non-lactating female between the ages of 18 and 65 inclusive on the day of dosing.
3. Able and willing to comply and be available for all protocol procedures and follow-up for the duration of the study.
4. Body Mass Index (BMI) of  $\geq 18.5$  and  $\leq 35$  kg/m^2.
5. Females of child-bearing potential must have a negative serum pregnancy test at screening and negative urine pregnancy test on Day 1 prior to dosing.
  - A woman is considered of childbearing potential unless post-menopausal ( $\geq 1$  year without menses) or surgically sterilized via bilateral oophorectomy, or hysterectomy or bilateral tubal ligation.
6. If the subject is female and of childbearing potential, she agrees to practice abstinence from sexual intercourse with men or use medically effective contraception (methods with a failure rate of  $< 1\%$  per year when used consistently and correctly) during participation in the study. Acceptable methods include:
  - Hormonal contraception including implants, injections or oral

## Statistical Analysis Plan (SAP)

---

- Two barrier methods, e.g., condom and cervical cap (with spermicide) or diaphragm (with spermicide)
  - Intrauterine device (IUD) or intrauterine system
7. Screening clinical laboratory results within normal ranges or are no greater than a Grade 1 and deemed not clinically significant by Medical Monitor (MM) and Principal Investigator (PI). Any subjects with results that are Grade 2 or above according to Common Terminology Criteria for Adverse Events (CTCAE) v5.0 will be excluded.
- Laboratory values that are outside the range of eligibility but are thought to be due to an acute condition or due to laboratory error may be repeated once.
8. The urine drug screen is negative.
- For Cohorts 1-3, if a subject has a positive urine drug screen that the PI believes is caused by a currently prescribed medication, (except for THC), the PI may enroll the subject if they meet all inclusion criteria, and none of the exclusion criteria.
  - For Cohort 4, if a subject has a positive urine drug screen that the PI believes is caused by a currently prescribed medication or positive for THC, the PI may enroll the subject if they meet all other inclusion criteria and none of the exclusion criteria.
9. Breathalyzer test is negative.
10. Available for follow-up for the duration of the study.
11. Agrees not to participate in vigorous activity 2 days prior to dosing and 2 days post-dose Day 1 and Day 45 for Cohorts 1-3 and Day 1 for Cohort 4, per Investigator discretion.

### 3.2.2 Exclusion Criteria

Subjects meeting any of the following exclusion criteria are not eligible for participation. All must be answered no for the subject to be eligible for study participation.

1. History of a chronic medical condition that would either interfere with the accurate assessment of the objectives of the study or increase the risk profile of the subject.
  - Chronic medical conditions include but are not limited to diabetes; Asthma requiring use of medication in the year before screening; Autoimmune disorder such as lupus, Wegener's, rheumatoid arthritis, thyroid disease; coronary artery disease; chronic hypertension; History of malignancy except low-grade (squamous and basal cell) skin cancer thought to be cured; chronic renal, hepatic, pulmonary, or endocrine disease (except previous asthma which has required no treatment for the past year).
2. Known history of severe allergic reaction of any type to medications, bee stings, food, or environmental factors or hypersensitivity or reaction to immunoglobulins.
  - Severe allergic reaction is defined as any of the following: anaphylaxis, urticaria, or angioedema.

## Statistical Analysis Plan (SAP)

---

3. Known allergic reactions to any of the study product components present in the formulation or in the processing.
4. A marked baseline prolongation of QT/QTc interval (e.g., repeated demonstration of a QTc interval >450 milliseconds).
5. Clinically significant abnormal electrocardiogram (ECG) at screening.
  - Clinically significant abnormal ECG results include but are not limited to: complete left or right bundle branch block; other ventricular conduction block except for incomplete RBB; 2nd degree or 3rd degree atrioventricular (AV) block; sustained ventricular arrhythmia; sustained atrial arrhythmia; two Premature Ventricular Contractions in a row; pattern of ST elevation felt consistent with cardiac ischemia; or any condition deemed clinically significant by a study investigator.
6. Positive serology results for human immunodeficiency virus (HIV), hepatitis B surface antigen (HBsAg), or hepatitis C virus (HCV) antibodies.
7. Febrile illness with temperature  $\geq 38^{\circ}\text{C}$  within 7 days of dosing. Subjects with acute febrile illness within 7 days of dosing may be rescreened no earlier than 7 days following resolution of symptoms.
8. Female subjects that are pregnant or breastfeeding or intending to become pregnant within the projected duration of the trial starting from the Screening visit until last dose.
9. Donation of blood or blood product within 56 days of enrollment.
10. Is currently participating or has participated in a study with an investigational product (IP) within 28 days preceding Day 1 (documented receipt of placebo in a previous trial would be permissible for trial eligibility).
11. Plans to enroll in another clinical trial that could interfere with safety assessment of the investigational product (IP) at any time during the study period.
  - Includes trials that have a study intervention such as a drug, biologic, or device only.
12. Treatment with a mAb (monoclonal antibody) within 3 months of Day 1.
13. Receipt of antibody (e.g., tetanus immune globulin (TIG), varicella zoster immune globulin (VZIG), intravenous immunoglobulin (IVIG), IM gamma globulin) or blood transfusion within 6 months or within 5 half-lives of the specific product given.
14. Reported active drug or alcohol or substance abuse/independence or illicit drug use that, in the opinion of the Investigator, would interfere with adherence to study requirements.
15. Use of H1 antihistamines or beta-blockers within 5 days of dosing Day 1 and Day 45 for Cohorts 1-3 and Day 1 for Cohort 4 (PRN use could be allowed with MM approval).
16. Use of any prohibited medication within 28 days prior to study entry or planned use during the study period.

## Statistical Analysis Plan (SAP)

---

- Note: Prohibited medications include immunosuppressives (except nonsteroidal anti-inflammatory drugs [NSAIDs]); immune modulators; oral corticosteroids (topical/intranasal steroids are acceptable); anti-neoplastic agents.
17. Previous exposure to botulinum toxin, receipt of antibodies against botulinum toxin, or previous treatment with equine antitoxin.
18. Any previous injection or planned injection within 4 months after enrollment of botulinum toxin for cosmetic reasons, spastic dysphonia, torticollis, or any other reason.
19. Any illness or condition that in the judgment of the Investigator may affect the safety of the subject or the evaluation of any study endpoint.
20. Is a study site employee, staff, or close relative as defined.
- PIs, Sub-Investigators
  - Staff who are supervised by the PI or Sub-Investigators
  - Member of the team conducting this clinical trial
  - Children, spouse, partners, siblings, and parents of site staff

### 3.3 Randomization and Blinding

For Cohorts 1-3, eligible subjects will be randomized to one of the 5 parallel treatment groups (50 mg G03-52-01 Lots 1 and 2, 100mg G03-52-01 Lots 1 and 2, and Placebo) in a 1:1:1:1:1 ratio, respectively, via the centralized randomization using Interactive Response Technology (IRT) randomization system (Table 1). Cohort 1-3 subjects will receive one dose of either G03-52-01 or Placebo on Days 1 and 45 for a total of two doses. No stratification will be performed for randomization.

For Cohort 4, eligible subjects will be randomized into one of 2 treatment groups (100 mg G03-52-01 or Placebo) in a 4:1 ratio. Cohort 4 subjects will receive one dose of either G03-52-01 or Placebo on Day 1. No stratification will be performed for randomization.

The ICON Randomization Development Team will generate the randomization schedule according to the sponsor protocol number G03-52-01-002, V4.0, 14Apr2024. The ICON team will deliver dummy and live randomization schedules to the IVRS System Development Team via a password-protected .zip file sent through e-mail.

The study staff participating in the administration of study product and assessment of the subjects and the subjects will be refrained from understanding the contents of the IM vial and are blinded from the study product information. Please refer to the Cohorts 1-3 Randomization Plan, v1.0, 16May2022 and Cohort 4 Randomization Plan, v1.0, 18Apr2024 for the detailed randomization list preparation and implementation.

The Investigator may unblind a subject's treatment assignment only in the case of an emergency or a serious adverse event (SAE) when knowledge of the study treatment is essential to the appropriate clinical management or welfare of the subject. Whenever possible, the Investigator should first discuss the options

## Statistical Analysis Plan (SAP)

---

with the ICON IGP Medical Monitor (MM) and the Resilience Government Services, Inc. Medical Lead (ML) or appropriately designated Resilience Government Services, Inc. personnel before unblinding the subject's treatment assignment. If this is impractical, the Investigator must notify the MM and the ML as soon as possible but without revealing the subject's treatment assignment. The date and reason for unblinding must be recorded on the SAE form.

Unblinding will be conducted through the IRT system. Notification to Resilience Government Services, Inc., ML, MM, unblinded statistician(s), and ICON clinical trial manager will be made for each unblinding, and a record will be kept at each study site for all unbroken treatment codes and the reason for the need to break the treatment assignment.

Vital sign assessments will be performed at all in-clinic study visits, including systolic and diastolic blood pressure (BP), heart rate (HR), and oral temperature. During screening and follow-up, a measurement that is a Grade 1 (as referenced in Protocol G03-52-01-002, v4.0, 14Apr2024, Appendix B) may be repeated once if the principal investigator believes a transient condition led to the aberrant value. Vital signs obtained at screening will serve as baseline values for the subject. Grade 1 values are allowable unless deemed clinically significant by the study Investigator.

- **Electrocardiogram (ECG)**

A 12-lead ECG will be performed at screening and reviewed by the study PI or a co-Investigator to assess the cardiac status of a subject for eligibility for enrollment.

- **Laboratory Evaluations**

Laboratory assessment schedule will follow the Schedule of Assessments in Appendix A. Detailed laboratory tests can be found in Section 8.5.2 of Protocol G03-52-01-002, v4.0, 14Apr2024.

- **Pharmacodynamic (PD) and Pharmacokinetic (PK) Assays**

Blood samples for PD assessment will be collected at pre-dose, 24 hours post-dose, and on Days 8, 15, 45 (prior to dosing) 49, 90, and 120 for all subjects in Cohorts 1-3. The first 25 subjects randomized for each DP lot of 50 mg and 100 mg doses and placebo will be tested at all 8 timepoints. The remaining samples from the subjects who received either dose or lot of G03-52-01 (including placebo) will only be tested using MNA at pre-dose and Days 45, 90, and 120.

Blood samples for PD assessment will be collected at pre-dose, 2 hours, 4 hours, 8 hours, 24 hours, and on Days 30, 45, and 90 for all subjects in Cohort 4. Cohort 4 samples for the first 30 subjects, who receive active drug product and complete sample collection at 24 hours, will be tested at pre-dose, 2 hours, 4 hours, 8 hours, 24 hours, and on Days 30, 45, and 90. PD samples will be analyzed for neutralizing antibody concentration (NAC) using the validated Battelle MNA.

Blood samples for PK assessment will be collected at pre-dose, 24 hours and 72 hours post-dose, and on Days 8, 15, 45 (prior to dosing), 49, 90, and 120 for all subjects in Cohorts 1-3. The first 25 subjects randomized for each DP lot of 50 mg and 100 mg doses and placebo will be tested at all timepoints.

Blood samples for PK assessment will be collected at pre-dose, 2 hour, 4 hours, 8 hours, 24 hours, 72 hours post-dose, and on Days 8, 15, 30, 45, 90, and 120 for all subjects in Cohort 4. Cohort 4 samples for the first 30 subjects, who receive active drug product and complete sample collection at 24 hours, will be tested at pre-dose, 2 hour, 4 hours, 8 hours, 24 hours, 72 hours post-dose, and on Days 8, 15, 30, 45, 90, and 120. The PK analysis of each mAb will be assessed using a validated electrochemiluminescence assay (ECLA) or enzyme-linked immunosorbent assay (ELISA).

- **Anti-Drug Antibody Assay (ADA)**

## Statistical Analysis Plan (SAP)

---

Blood samples will be collected for all subjects in Cohorts 1-3 at pre-dose and Days 15, 45 (prior to dosing), 60, 90, 120, 150, 180, and 240 and pre-dose and post-dose on Days 90, and 120 for all subjects in Cohort 4 for determining the presence of ADA using a validated ECLA that measures total ADA in serum. This will be performed to assess immunogenicity.

### 4 Types of Planned Analyses

#### 4.1 Interim Analyses

An interim analysis is planned for the first 125 subjects in Cohorts 1-3 who complete through Day 120. An interim Clinical Study Report (CSR) is planned for the same 125 subjects across the three cohorts through Day 120. The data cut will take place when all 125 subjects have completed their 120 visits. The safety analysis will include all available safety data obtained from all subjects enrolled in the study up to the time of the fourth Data Safety Monitoring Board (DSMB) meeting.

The objectives of this interim analyses will be to compare safety between the 3 cohorts and to evaluate lot-to-lot variation in PK and PD parameters within the two active drug cohorts.

#### 4.2 Data Safety Monitoring Board

A centralized, independent DSMB will be established in collaboration with Resilience Government Services, Inc. and ICON and will oversee the safety conduct the study. The DSMB will make safety and tolerability recommendations.

Following data and documents will be generated for DSMB review:

- Incidences and listings of overall Adverse Events (AEs), Medically Attended Adverse Events (MAAEs), and Serious Adverse Events (SAEs)
- Summaries and listings of change from baseline in electrocardiogram, vital signs, and clinical safety laboratory values
- Other relevant data / documents:
  - Number of enrolled subjects
  - Number of subjects withdrawn and subject dispositions
  - Subject characteristics and anthropometric measures data (including age, height, weight, and BMI)
  - Protocol deviations will be summarized. Listings for Per-Protocol (PP) population will not be available for DSMB meetings and there will not be DSMB analyses based on the PP population.

Blinded tables, figures, and listings (TFLs) will be provided for the open session of DSMB meetings. A dummy randomization schedule will be used to assign the subjects to groups, whereby subjects will be summarized in their true treatment group, but treatment groups will be arbitrarily labeled and ordered in tables to preserve the blind.

Four DSMB meetings are planned for Cohorts 1-3, and one DSMB meeting is planned for Cohort 4.

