9.13. Safety Oversight

9.13.1. ICON Medical Monitor

The ICON MM is the clinical site's primary point of contact for eligibility or safety related questions. The ICON MM is responsible for liaising with RGS ML to ensure that all medical concerns are communicated and will provide any potential pertinent medical communication update to the project team as needed. As well as make a recommendation that the DSMB be convened to review any safety concerns.

The ICON MM will communicate with the RGS ML for any safety related questions. The ICON MM will participate in the planned DSMB meetings and make recommendations that the DSMB be convened to review any safety concerns.

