9.13.2. Resilience Government Services (RGS) Medical Lead

The RGS ML will be the main point of contact for the ICON MM including any safety-related questions or concerns. The RGS ML will escalate any medical or safety concerns to the DOD as needed. The RGS ML will participate in the planned DSMB meetings and can make a recommendation that the DSMB be convened to review any safety concerns.

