### 9 Statistical Methods

#### 9.1 General Statistical Conventions

All statistical procedures will be completed using SAS version 9.4 or higher.

Unless otherwise stated, all statistical testing will be two-sided and will be performed using a significance (alpha) of 0.05. Two-sided 95% confidence intervals (CI) will be provided where relevant.

Continuous variables will be summarized using descriptive statistics, including number of subjects (n), mean, median, standard deviation (SD), first quartile (Q1), third quartile (Q3), minimum, and maximum. Means, medians, and quartiles (if averaged value) will be rounded to one more decimal place than what is reported in the data. SDs will be rounded to two more decimal places than what is reported in the data.

For categorical variables, summaries will include counts of subjects and percentages. Percentages will be rounded to one decimal place.

For summary purposes, baseline is defined as the last measurement prior to the first treatment administration. All summaries will be presented by treatment group and for all subjects, unless otherwise specified.

All subject data, including those derived, will be presented in individual subject data listings. Unless otherwise stated, unscheduled visit results will be included in date/time chronological order within subject listings. All listings will be stratified by treatment group and sorted by subject ID in ascending numerical order, and date/time in ascending chronological order. The subject's race, sex, and age will be stated on each listing. Unless otherwise stated, data listings will be based on all randomized subjects (ITT Population).

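### In Cohort 4 the 4:1 allocation lets group size reveal the placebo column in open-session DSMB tables, so dummy labels do not keep the blind

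*SAP*

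**What the plan says.** SAP 4.2 fixes both the form and the audience of the output: "Blinded tables, figures, and listings (TFLs) will be provided for the open session of DSMB meetings". A dummy randomization schedule is used, but the same sentence adds that "subjects will be summarized in their true treatment group, but treatment groups will be arbitrarily labeled and ordered in tables to preserve the blind". Only the names and the order of the columns are masked. The listed content includes incidences and listings of adverse events, numbers enrolled, and dispositions. On frequency, the section says that "one DSMB meeting is planned for Cohort 4", without giving its timing.

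SAP 3.1 describes Cohort 4 as having two groups, "with 200 subjects randomized into the active group (Cohort 4 100 mg G03-52-01) and 50 subjects randomized into the Cohort 4 Placebo group". SAP 3.3 repeats the 4:1 ratio. Cohorts 1-3, by contrast, are five equal groups of about 75.

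SAP 9.1 sets the general display rules: "For categorical variables, summaries will include counts of subjects and percentages". It also has listings arranged by treatment group and then by subject ID.

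On attendance, Protocol 9.13.1 says "The ICON MM will participate in the planned DSMB meetings" and Protocol 9.13.2 says "The RGS ML will participate in the planned DSMB meetings". Protocol 5.4.2 keeps everyone with access to subjects or their data blinded until the data are verified and the database is locked.

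**The concern.** Arbitrary labels hide which column is which only when the columns look alike. In Cohort 4 one column has about four times as many subjects as the other, so the labels carry no protection. Neither document makes an exception for Cohort 4, although the SAP's revision history shows that its section on planned analyses was updated when Cohort 4 was added.

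The two named attendees have continuing roles in the trial. The medical monitor is the sites' contact for eligibility and safety questions (Protocol 9.13.1). The monitor reviews data for a possible halt of dosing in consultation with the medical lead (Protocol 9.12.1). Where possible, investigators consult both before an emergency unblinding (Protocol 5.4.4). If they know which column is placebo, they hold Cohort 4 safety results by arm while still counted as blinded.

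**Working it through.** **1. Plan's own figure.** 250 subjects at 4:1 gives 250 × 4/5 = 200 active and 250 × 1/5 = 50 placebo. This reproduces SAP 3.1.

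**2. Is group size visible?** A count shown with its percentage gives the denominator even if no N is printed. For example, 10 subjects with an event would appear as 10/200 = 5.0% in one column, and 10 in the other as 10/50 = 20.0%.

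**3. How often does size point to the right arm?** The number of Cohort 4 subjects at the DSMB cut is not stated, so *n* is varied as an assumption. Under simple randomization the number on active drug is X ~ Binomial(n, 0.8). The smaller group fails to be placebo when X < n/2; a tie is counted as one half.

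| n in the cut | P(active group strictly larger) | P(smaller group is not placebo), ties split |
|---|---|---|
| 10 | 0.967 | 2.0% |
| 25 | 0.99963 | 0.037% |
| 50 | 0.999998 | 1.3 in a million |
| 250 | 1.000 | 2.5 × 10⁻²⁶ |

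The two probability columns do not sum to one for even n because of ties. A working mask would leave an attendee at 50%. A blocked 4:1 list would hold the sizes closer to 4:1 and make identification more certain.

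**4. What an attendee can conclude from one table.** For observed sizes a > b and equal prior weight on the two labellings, the likelihood ratio that the larger group is active is

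(0.8^a × 0.2^b) / (0.2^a × 0.8^b) = 4^(a−b),

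so the posterior probability is 4^(a−b) / (1 + 4^(a−b)). At 8 versus 2 this is 4⁶/(1 + 4⁶) = 4096/4097 = 0.9998. At 16 versus 4 it exceeds 0.9999999. At 200 versus 50 it is certain for practical purposes.

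**5. Contrast with Cohorts 1-3.** Five groups of 375/5 = 75 give no clue from size. If lots were pooled within dose, the columns would be 150, 150 and 75, and placebo would again stand out.

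**6. Listings.** SAP 4.2 speaks of arbitrary labels and order in tables and does not say whether open-session listings carry a group. If they follow the SAP 9.1 arrangement by treatment group, identifying the column also identifies each listed subject's assignment. If they carry no group, only arm-level results are exposed.

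**The case against.** The strongest reply concerns consequence. A reader might infer that adverse event assessment in Cohort 4, and so a primary endpoint, is no longer blind. The documents do not support that. Severity and relationship are rated by the investigator (Protocol 9.9.1 and 9.9.2), and the contractor's drug safety physician adds a causality assessment for SAEs (Protocol 9.10.2). Neither document gives causality to the medical monitor or medical lead, and none of the text places site investigators in DSMB meetings.

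A reader might also infer that all 250 Cohort 4 subjects, 250/625 = 40% of the trial, are affected. That is not shown either. There is one dose and one DSMB meeting, and only judgements made after that meeting could be influenced. If follow-up is nearly complete by then, little remains.

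Unblinding of individual subjects cannot be stated flatly; it depends on how listings are labelled. The trial has no formal hypothesis test, and the Cohort 4 neutralizing-antibody endpoints are laboratory assays. All of this stands and limits the point.

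Two further replies are weaker. The DSMB charter and table shells were not available, and they might suppress denominators or pool the arms. However, the SAP states its method without any such condition. It could also be said that the dummy schedule reassigns subjects at random, which would remove the leak. The same sentence says that subjects stay in their true group.

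**Conclusion.** The masking described in SAP 4.2 does not deliver the property it claims for Cohort 4. At any realistic size of the data cut, the placebo column can be identified with near certainty. The medical monitor and the medical lead could therefore learn arm-level Cohort 4 results before database lock, which conflicts with Protocol 5.4.2.

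This rests on three assumptions: open-session output for Cohort 4 is split by arm with sizes visible or derivable; the two attendees are present for at least the open session; and allocation is simple or blocked at 4:1. The protocol supplied is dated 12 Apr 2024, whereas the SAP cites version 5.0 of 06-JAN-2025, so the attendance and blinding text should be checked against that version.

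The probabilities above measure how surely the arm is identified. They are not an estimate of bias. Planned estimates and analysis populations do not change, and the exposure is limited to eligibility and safety advice, consultation on emergency unblinding, and halting review after the single Cohort 4 meeting.

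**What to change.** - **SAP 4.2 and DSMB charter:** present Cohort 4 open-session tables pooled over arms, and its listings without any group identifier.
- **By-group output:** give it only to DSMB members, in a closed session, through the unblinded statistician, a role that Protocol 9.13.3 already mentions.
- **Protocol 9.13.3:** it now describes the board as reviewing safety data that are blinded yet split by group. Align it with the two-session arrangement, since neither document describes what a closed session receives.
- **Cohorts 1-3:** state that dummy labels are adequate only while the five equal groups are shown unpooled.
- **If the Cohort 4 meeting has already been held:** record who received by-group output and report it in the CSR.

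The cost is a small edit to the SAP, charter and shells, plus a specification of the closed-session package. The sponsor would see no by-group Cohort 4 data in the open session. No analysis or sample size changes.
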